## 3.8 Statistical Considerations

**3.8.1 Descriptive and Exploratory Analyses:** The initial analyses of the data will be descriptive in nature. Using means, standard deviations, median, and range, the distribution volume ratios (DVRs) will be described for each time point before and after subjects have used the nutritional supplementation for approximately 90 days. Similarly, the clinical scores will be described for each time point. Graphical methods, such as plots of measurements over time, histograms, and boxplots are important tools for understanding the quality of the data, and assessing assumptions underlying statistical models (such as normality). Transformations will be applied as necessary to satisfy these assumptions. Plots of all of the measured variables over time will be important to assess longitudinal patterns of change.

**3.8.2 Analyses for Primary Objectives:** To evaluate whether intravenous/oral NAC helps to support dopamine function in the brain of patients with PD by measuring changes in the dopamine transporter. To accommodate the longitudinal nature of the data, a Heterogeneous Random Coefficients Model (62,63) will be fit for the DVRs in each region for the DaTSCAN binding and each neurobehavioral score (i.e. UPDRS scores). This model can also account for both between and within subject heterogeneity and will accommodate modeling potentially nonlinear therapeutic effects over time. The random coefficients model is more flexible in terms of modeling the changes in DVRs and neuropsychological tests over time than repeated measures analyses of variance. The random coefficients model also has fewer restrictions on the correlation structure between multiple measures within subjects. ANCOVA will be used in order to determine if there are correlations between the pre-intervention neuropsychological and clinical measures and the longitudinal outcome measures after receiving oral or intravenous supplementation. This analysis will also evaluate whether the DaTSCAN DVRs can be utilized as a predictor for outcome. To determine if there is a correlation between changes in DAT binding and symptom severity, Pearson product-moment correlations will be computed unless the normality assumption is violated, in which case the Spearman rank correlation will be computed.

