## **3.0 STUDY PLAN**

### **3.1 Subject Recruitment**

[figure not shown]
Subjects may be pre-screened by telephone using a standardized script and screening form. Verbal consent and HIPAA Authorization to obtain the prescreening information will be obtained from subjects prior to the prescreening interview. If subjects are prescreened in person, a signed consent and HIPAA Authorization to obtain prescreening information will be obtained. Information collected during pre-screening will be incorporated into the research records as source documentation for subjects included in the study. If subjects are not eligible to participate in the study they will be asked if the information provided in during prescreening maybe retained for consideration in other studies. Prescreening information will be retained for an indefinite period on an official screening form that will be kept in a secure locked area that will only be used by persons involved with research with this research Study.

We plan on recruiting up to 65 subjects over 3 years with the goal of recruiting 28 subjects who will receive approximately 90 days of combined intravenous/oral NAC, and then 14 subjects who will be in the waitlist control group receiving standard of care to be evaluated initially and then approximately 90 days later. This will allow for an attrition rate of up to one third. At the conclusion of the study, those in the waitlist control group will be given the option to receive a trial of oral/intravenous NAC if the data suggests that NAC is effective. All of the study subjects must be clinically diagnosed with PD by a referring neurologist. Subjects may be assessed using

structured examinations (i.e., the Unified Parkinson's Disease Rating Scale (UPDRS) or Movement Disorder Society (MDS) Unified Parkinson's Disease Rating Scale (MDS-UPDRS) and/or the Hoehn and Yahr scale. Diagnostic criteria will be applied using structured questionnaires, clinical interviews, and neurological examinations. Additional information is gathered, whenever possible, from family members, caregivers, review of previous medical records, and physical and laboratory examination. Subjects may take PD medications, but must be on a stable dose for at least 1 month prior to entering into the study.

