### 3.3 Treatment Plan:

3.3.1 Informed consent will be obtained from all subjects before protocol specific activities are carried out. The subject will be informed about the limited data on oral supplementation and intravenous/oral NAC to support brain health in PD patients, possible risks and benefits, and possible adverse events. Informed consent will be documented by use of written consent form approved by the Institutional Review Board at Thomas Jefferson University and signed by the subject or the subject's legal guardian. History, physical and neurological examination, and initial SPECT and MRS procedures (see below) will begin within 14 days of the informed consent process. Subjects will be receive either intravenous/oral NAC, or be placed on the waitlist control.

After approximately 90 days of receiving the supplements, subjects will undergo a follow up evaluation, which includes repeat neurological assessments, SPECT, and MRS. Note that subjects will continue taking the oral NAC until the scans are completed. Subjects will also continue to take their current Parkinson's medication regimen so that they will continue to receive standard of care treatment throughout the study. It is hoped that their standard of care treatment will remain constant throughout the course of the study, but their referring neurologist may adjust their medications as medically necessary.

3.3.2 N-Acetylcysteine will be obtained from the Jefferson Pharmacy (NAC is also called Acetadote; Cumberland Pharmaceuticals). NAC is an intravenous (IV) medication for the treatment of acetaminophen overdose. Acetylcysteine is the nonproprietary name for the N-acetyl derivative of the naturally occurring amino acid, L-cysteine (N-acetyl-L-cysteine, NAC). Acetadote is supplied as a sterile solution in vials containing 200 mg/mL acetylcysteine. The pH of the solution ranges from 6.0 to 7.5. Acetadote contains the following inactive ingredients: 0.5 mg/mL disodium edetate, sodium hydroxide (used for pH adjustment), and Sterile Water for Injection, USP.

For the oral supplement, NAC is obtained by the Jefferson Pharmacy at [name] and supplied by Vital Nutrients (produced under GMP) as a 600mg capsule of N-acetyl cysteine. The following inactive ingredients are also included: Ascorbyl Palmitate, Gelatin, Rice, Silica. The capsules contain no coatings, binders, fillers, or dairy, wheat, eggs, soy, yeast, commercial sugars, starch, preservatives, or hydrogenated oil.

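### With only two visits, the 3.8.2 model cannot show nonlinear effects, 3.8.4 names different analyses, and no baseline-adjusted NAC-versus-waitlist contrast is stated

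*Combined protocol and SAP*

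**What the plan says.** **Visits.** Section 3.1 has the waitlist arm receiving "standard of care to be evaluated initially and then approximately 90 days later". Section 3.3.1 says: "After approximately 90 days of receiving the supplements, subjects will undergo a follow up evaluation". Sections 3.4.1, 3.7 and 3.7.1 agree for endpoints, clinical scales and scans. No other outcome visit is scheduled.

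**Model.** Under the primary objective, 3.8.2 states that "a Heterogeneous Random Coefficients Model (62,63) will be fit for the DVRs in each region for the DaTSCAN binding and each neurobehavioral score". It says the model "will accommodate modeling potentially nonlinear therapeutic effects over time", is "more flexible in terms of modeling the changes in DVRs and neuropsychological tests over time than repeated measures analyses of variance", and "also has fewer restrictions on the correlation structure between multiple measures within subjects". It does not list the random effects, an arm term or an arm-by-time term.

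**ANCOVA.** It appears in 3.8.2 for a different purpose: "ANCOVA will be used in order to determine if there are correlations between the pre-intervention neuropsychological and clinical measures" and later outcome.

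**Other analyses.** Section 3.8.4 says the analyses are a two-way repeated measures ANOVA and linear regression, does not mention the random coefficients model, gives no covariates, and claims both methods have more power than the t-tests behind the sample size. The SPM analysis in 3.8.3 compares baseline with post-treatment scans.

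**The concern.** Section 3.8.2 prefers the random coefficients model to repeated measures ANOVA for features that need more than two measurements per subject or leave its variance parameters undetermined. Section 3.8.4 then names the method that 3.8.2 argued against. A statistician with the locked data would have to decide which analysis is primary and whether baseline DVR enters it.

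Two things are at stake. One is precision: baseline scans are collected from everyone, and 3.8.4 wants this pilot to supply the effect size for larger trials. The other is pre-specification: a change-score test and a baseline-adjusted test can disagree, and leaving the choice open until the data are seen inflates the error rate.

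**Working it through.** **1. The plan's own figure.** Inputs from 3.8.4: variability 10%, effect 5–10%, 80% power, p = 0.05, 28 and 14 subjects. Two-sided testing is my assumption. A two-sample t-test with SD 10 and 2:1 allocation at a 10% difference needs 26/13, close to 28/14. With 28/14 the power is 85% at 10% and 32% at 5%. The t-test arithmetic is therefore the right starting point, at the upper end of the effect range.

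**2. Nonlinear time effects.** Intercept, linear and quadratic time at two time points give a design of rank 2 for 3 terms. Curvature is not estimable.

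**3. Variance components.** With times 0 and 1, a correlated random intercept and slope plus residual error has 4 parameters (g00, g01, g11, s²). Two visits supply 3 moments:
- Var(Y0) = g00 + s²
- Cov = g00 + g01
- Var(Y1) = g00 + 2·g01 + g11 + s²

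For (g00, g01, g11, s²), the sets (1, 0, 0.5, 0.2) and (1.1, −0.1, 0.7, 0.1) both give variances 1.2 and 1.7 and covariance 1.0. In a simulated data set of 42 subjects the profile log-likelihood was identical at residual variances 2, 6, 10 and 15. Letting the visit day vary with an SD of 8% of the interval moved it by only about 0.55. The fixed group-by-time effect is unaffected.

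**4. Change score against ANCOVA.** SE = SD × √(1/28 + 1/14) = 0.327 × SD, with 40 df for the change score and 39 for ANCOVA. The protocol gives no baseline-to-follow-up correlation (rho), so 0.5 to 0.9 is assumed, with equal visit SDs and complete data. It does not say what the 10% refers to, so both readings are shown.
- Reading A, 10% is the SD of change: ANCOVA SD = 10 × √((1 + rho)/2).
- Reading B, 10% is the single-visit SD: change SD = 10 × √(2(1 − rho)); ANCOVA SD = 10 × √(1 − rho²).

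Power at a 5% difference, change score → ANCOVA:

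| rho | Reading A | Reading B |
|---|---|---|
| 0.5 | 32% → 41% | 32% → 41% |
| 0.7 | 32% → 37% | 49% → 55% |
| 0.8 | 32% → 35% | 65% → 70% |
| 0.9 | 32% → 33% | 91% → 93% |

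Simulation of 40,000 trials, which allows for chance baseline imbalance, gives ANCOVA values 0 to 2 points lower. At a 10% difference and rho 0.5/0.7/0.8, power goes from 85% to 93/90/88% (A) or from 85/97/>99% to 93/99/>99% (B). The 95% CI half-width at the same three correlations goes from 6.6 to 5.7/6.1/6.3 percentage points (A) or from 6.6/5.1/4.2 to 5.7/4.7/4.0 (B). At rho 0.9 under B it moves only from 2.96 to 2.89.

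**5. Choosing after the data are seen.** In null simulations each test alone holds about 5%. Always reporting the smaller p-value of change score and ANCOVA gives about 6.3–7.4% over rho 0.5 to 0.9. At a true 5% difference under B, the two disagree on significance in about 17/14/10/3% of trials.

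**6. The power claim in 3.8.4.** With two visits and complete pairs, the repeated measures ANOVA group-by-time test is the change-score t-test, so it cannot have more power than that test. Against a follow-up-only t-test it gains when Var(change) < Var(follow-up), that is, when rho > SD_baseline / (2 × SD_follow-up). The threshold is 0.5 with equal visit SDs, 0.625 if the follow-up SD is 0.8 times baseline, and 0.417 if it is 1.2 times.

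**The case against.** The strongest reply is that little of this touches the arm comparison. The identification problem depends on which coefficients are random, and 3.8.2 does not say. With uncorrelated intercept and slope there are 3 parameters for 3 moments, so the model is formally identified, though only through an unstated assumption that depends on where time zero is placed. The remark on nonlinearity describes a model class; no nonlinear term is planned. With complete pairs and equal arm variances, a random-intercept fit gives the same group-by-time test as repeated measures ANOVA, so the conflict between 3.8.2 and 3.8.4 is partly one of names. Section 3.1 does allow for heavy loss ("This will allow for an attrition rate of up to one third"), and missing follow-up scans make the two differ. In simulations with 43/22 enrolled and 28/14 followed up (rho 0.7, SD 10), the estimates differed by 0.46 on average, against an SE of about 2.5. This is a pilot, and a change-score contrast is unbiased under the 2:1 randomization. All of that stands, and it limits the point to precision and pre-specification.

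A reader might infer more than the documents support:
- **That the arms cannot be compared.** They can: the group-by-time effect is estimable from two visits.
- **That the error rate could reach about 10%.** Adding a follow-up-only regression on arm to the choices gives 9.5–10.3% at rho 0.5–0.8. That option fits poorly with objective 2.1.2 and section 3.8.2, both of which are about changes in the transporter, so I do not count it.
- **That the power sentence in 3.8.4 is false.** The t-test is not named. If it is follow-up-only, the claim for repeated measures ANOVA holds whenever rho exceeds 0.5 with equal visit SDs. It is unsupported, not shown to be wrong.

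**Conclusion.** The point holds as a matter of specification and efficiency and should be fixed. Two visits cannot show nonlinear effects. A correlated random intercept and slope would leave slope and residual variance unseparated, apart from weak information in visit-day variation. Sections 3.8.2 and 3.8.4 name different analyses, and neither states a baseline-adjusted NAC-versus-waitlist contrast.

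The size is modest and depends on rho. ANCOVA's variance is (1 + rho)/2 of the change score's with equal visit SDs: 0.75, 0.85, 0.90 and 0.95 at rho 0.5, 0.7, 0.8 and 0.9. At a 5% difference that is a gain of about 9 power points at best and 1 to 2 at rho 0.9. The false-positive figure of about 6.3–7.4% is for one region and requires that the smaller p-value is always reported; nothing in the plan says that it will be. All figures assume 28/14 complete pairs, two-sided 0.05 and equal visit SDs. If the follow-up SD is 1.2 times baseline, the variance ratio is 0.87/0.97/0.997 at rho 0.5/0.7/0.8, so the gain nearly vanishes at the top of that range; at 0.8 times baseline it is 0.57/0.63/0.64 and the gain is larger.

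**What to change.** - In 3.8.2 and 3.8.4, name one primary analysis: ANCOVA of the 90-day DVR on arm and baseline DVR, for one region or summary chosen by the sponsor, reported as the adjusted NAC-minus-waitlist difference with its 95% CI. A two-visit mixed model with unstructured covariance and a common baseline mean is an acceptable equivalent.
- Use the same form for UPDRS and the other scores.
- State that repeated measures ANOVA and the random coefficients model are not competing primary analyses. If the latter is kept as secondary, say which coefficients are random and what is heterogeneous.
- Delete the nonlinear-effects wording.
- Delete the claim of greater power than t-tests, or qualify it by naming the t-test, the assumed rho and the visit SDs.

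The cost is one degree of freedom and protocol wording; no new data, visits or subjects are needed.

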### 3.7. Clinical Response

Subjects will be evaluated utilizing the UPDRS scores to determine any improvements in PD symptoms. Subjects will also be evaluated using the Profile of Moods Scale, Beck Depression Inventory, Mini-Mental Status Exam, and Parkinson's disease Questionnaire-39. These will be obtained initially and after approximately 90 days of taking the supplements.

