Manual demarcation of brain regions - A set of standardized templates containing small ROIs will be fit on each DaTSCAN. Within the x-y plane, small ROIs in the template will be smaller than the actual structures they represent in order to minimize resolution-induced problems with ill-defined edges. To reduce the effects of volume averaging in the axial direction, the small ROIs will not be placed on the slices that contained the upper most and lower most portions of the structures they represent. This will tend to limit the small ROIs to the central aspect of structures they represent. The primary outcome measure will be the specific uptake values at 3 to 4 hours post administration, when the distribution of DaTSCAN has approached a transient, near equilibrium like state that reflects the ratio of  $k_3/k_4$ , which is related to binding potential. This allows for a quantitative assessment of dopamine transporter activity. Again, scanning at this time of a pseudo-equilibrium state allows for quantitative analysis using a region of interest analysis with a background region as an index of nonspecific binding.

As described above, it is probably not necessary to account for volumetric changes especially since the ROIs will be smaller than the actual structures. However, since all scans will have MRI correlation for adequate placement, volumes of the basal ganglia structures can be determined and utilized as an additional analysis. The reference region has typically been the cerebellum or the brain regions above the level of the basal ganglia, corresponding to areas of the brain, which have very low concentrations of DAT. However, values will be obtained for both whole brain regions above the basal ganglia and cerebellar regions in order to confirm the findings.

Statistical Parametric Mapping (SPM) will also be performed on the images in order to compare the pre- and post-intervention scans in PD subjects. SPM is currently considered to be a highly successful analytical tool for evaluating of SPECT brain images, and will be included in the analysis.

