**3.8.4 Power Analysis:** We view this study primarily as a pilot study to assess changes in physiological and clinical measures and determine the effect size for powering future, larger trials. However, we estimated the sample size needed based upon prior research we have performed evaluating DAT imaging in the study of PD patients. We have previously found that the PD patients can have variability in their DVR measures of dopamine binding of approximately 10%. If we expect a 5-10% improvement in the treatment groups, for an 80% power to detect a significant change of  $p=0.05$ , we would need approximately 28 subjects in the treatment arms and approximately 14 subjects in the control arm. The statistical analyses for the proposed study will consist of 1) repeated measures two-way ANOVA, and 2) linear regression. Both methods are more powerful than simple t-tests on which these estimates are based. Thus, we plan to recruit up to 65 subjects, to allow for attrition which could be as high as one third, who would then be randomized into the two groups in a 2:1 ratio until the groups are complete.

3.8.5 Randomization: Randomization will occur via a 2:1 ratio of the NAC group and the waitlist control groups using the method of random permuted blocks with random block sizes without stratification.

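### Section 3.8.2 models every regional DVR and every clinical score under the primary objective without naming the one test that decides it, so the 5% error rate and 80% power in 3.8.4 attach to no identifiable comparison

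*Combined protocol and SAP*

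**What the plan says.** - Section 3.8.2 states the primary objective in terms of the dopamine transporter. It then says that random coefficients models "will be fit for the DVRs in each region for the DaTSCAN binding and each neurobehavioral score (i.e. UPDRS scores"). It names no lead region, ranks no scores, states no significance level and does not say which model term decides the question.
- Section 3.7.1 gives the outcome by type: "The primary outcome measure will be the specific uptake values at 3 to 4 hours post administration". No region, side or striatal average is attached to it. Two reference regions are used: "values will be obtained for both whole brain regions above the basal ganglia and cerebellar regions in order to confirm the findings". No rule says what happens if they disagree.
- Section 3.7 lists, besides the UPDRS, the "Profile of Moods Scale, Beck Depression Inventory, Mini-Mental Status Exam, and Parkinson's disease Questionnaire-39".
- Section 2.0 lists clinical symptoms, transporter imaging and MRS as three objectives, without ranking them.
- Section 3.8.3 concedes that small ROIs lose specificity through multiple comparisons. It applies random-field and small-volume corrections to the SPM maps. No correction is given for the ROI models or the clinical scores.
- Section 3.8.4 calls the study primarily a pilot, then sizes it "for an 80% power to detect a significant change of" p=0.05, with 28 and 14 subjects. It bases this on simple t-tests. It also lists a two-way repeated measures ANOVA and linear regression as the analyses, which are not the model in 3.8.2.

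**The concern.** A 5% error rate and 80% power are properties of one specified comparison. Here several regional models and several clinical models share the primary heading, and the text does not say which of them answers the question. An analyst who follows the plan to the letter could see one region reach p<0.05 and the others not, with nothing in the plan to say whether the primary objective was met.

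This affects both uses of the study. If significance is claimed, the true error rate is above the nominal one by an amount that depends on how many regions and scores are run. If the study is used only to give an effect size for a later trial, choosing the most favourable region after seeing the data would inflate the estimate carried forward.

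**Working it through.** **Inputs from the documents.** Alpha 0.05, power 80%, 28 and 14 subjects, and a 2:1 ratio (3.8.4 and 3.8.5). Effect: "If we expect a 5-10% improvement in the treatment groups". Spread: "variability in their DVR measures of dopamine binding of approximately 10" percent, read as a standard deviation. Clinical instruments: UPDRS plus four others, so five if each gives one total score (3.7).

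**Assumptions.** Two-sided testing, because the plan does not state sidedness. Four regions, because the plan gives no number. Correlation between test statistics of 0, 0.5 or 0.8, because the plan gives none.

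**Step 1: the plan's own figure.** For a two-sample comparison at 2:1, control n = 1.5 × (1.96 + 0.8416)² × (SD/effect)² = 11.77 × (10/effect)².
- Effect 10%: 11.77, so 12 controls and 24 NAC.
- Effect 9.5%: 13.05, so 14 controls and 28 NAC.
- Effect 5%: 47.1, so 48 controls and 96 NAC.

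The stated 28 and 14 fit 80% power for **one** test at an effect of about 9.4% (exact t-test), not across the whole 5–10% range. That range is a separate sample-size question. What matters here is that the calculation is for a single comparison at 0.05.

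**Step 2: chance of at least one p<0.05 when NAC has no effect.** For k independent tests this is 1 − 0.95^k. For k = 4: 1 − 0.8145 = 0.185. For k = 9 (4 regions plus 5 scores): 1 − 0.6302 = 0.370. The correlated cases use equally correlated normal test statistics.

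| Tests counted | Independent | Correlation 0.5 | Correlation 0.8 |
|---|---|---|---|
| 1 named test | 5% | 5% | 5% |
| 4 regions, one reference | 19% | 16% | 11% |
| 4 regions + 5 scores, one reference | 37% | 27% | 17% |

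**Step 3: errors in NAC's favour only.** The benchmark for one test is 2.5%. For 4 regions with one reference the figure is 10% if independent, 8% at correlation 0.5 and 6% at 0.8. For 9 tests it is 20%, 13% and 8%.

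**Step 4: the second reference region.** Take 4 regions at correlation 0.5, and correlation 0.9 between references. If a result against either reference counts, the two-sided rate rises from 16% to 21%. If both must agree, it falls below the one-reference figure. The plan does not say which applies.

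**Step 5: keeping every test co-primary.** With Bonferroni, alpha per test is 0.05/4 = 0.0125 or 0.05/9 = 0.0056. At 28 and 14, SD 10% and a 10% effect (normal approximation), power per test falls from 86% to 71% or 61%. Naming one test avoids this loss.

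**The case against.** The strongest reply is that this is a pilot meant to estimate effect sizes, that the outcome type is already fixed in 3.7.1, and that the authors saw the ROI multiplicity problem and added a corrected SPM analysis. Much of this is fair. The pilot aim lowers the stakes. The transporter does lead by type: 3.8.2 words its objective around it, and no success rule says that a mood or cognition score would count. The reference to UPDRS in 3.8.2 may also mean fewer than five scores. What the reply does not supply is the region, the reference or the contrast. The SPM correction does not reach the ROI models or the scores, and 3.8.4 still sizes the trial for a significance test.

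Three stronger readings are tempting and should not be drawn.

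- **That a false positive is likely.** In every case tabulated above the chance is below one half. A favourable error on the transporter alone is about 6–10% with four regions.
- **That two reference regions double the number of tests.** Section 3.7.1 includes the second to confirm findings, and 3.8.3 already names the cerebellum as the background region. What is missing is the rule for disagreement.
- **That the two terms, specific uptake and DVR, give the planned improvement two sizes and so undermine the power.** Section 3.8.4 states the variability for DVR measures and gives the improvement in the next sentence. Nothing places that improvement on a specific-uptake scale. The mixed naming is a wording fault.

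**Conclusion.** The gap is real and of moderate weight. The primary analysis has a named modality but no named test, and outside SPM nothing limits the error across regions and scores. With four regions assumed, the two-sided false-positive rate is about 11–19% for the transporter alone with one reference, and about 17–37% once five clinical scores are counted, against a nominal 5%. These ranges run from correlation 0.8 to independence and would change with the true number of regions, which the documents do not give. The p=0.05 itself stands only in 3.8.4, so applying it to each model in 3.8.2 is an inference, though no other level is offered for those models. The pilot label softens the consequence without closing the gap.

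**What to change.** In 3.8.2, name one primary test: the between-arm difference in change at about 90 days in one pre-named DVR, at two-sided 0.05. A natural choice is the average over the striatal ROIs with the cerebellum as reference, since 3.8.3 already treats the cerebellum as the background region. Then:

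- make the second reference region a sensitivity analysis, and say how disagreement will be reported;
- list the regions, and label those outside the primary measure, together with all clinical scores, as secondary or exploratory, with confidence intervals;
- use one term, DVR or specific uptake, in 3.7.1, 3.8.2 and 3.8.4, and tie the power statement in 3.8.4 to the named test.

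This is a cheap improvement. It changes wording only and needs no new data, visits or subjects. Its one downside is that a positive result outside the named test can no longer be claimed as primary.
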